3.3 Instructions to Subjects

700 Subjects in all groups will be dispensed acetazolamide (see section 4.1) and receive dietary
701 counseling (see section 4.1.6). Acetazolamide should be started on the day of randomization
702 unless the Site Investigator deems delays occurring during the screening/baseline examination
703 may be harmful to the patient. In this case, the acetazolamide titration according to section
704 4.1.1.4 may be started prior to randomization.

705 For subjects in the two surgery groups, surgery should be performed as soon as possible, ideally
706 within 3 days of randomization, but not more than 7 days.

707

Chapter 4: Study Treatments

708

4.1 Medical Therapy including Diet

709

4.1.1 Acetazolamide

710

4.1.1.1 Acquisition

711 Taro Pharmaceutical Industries will supply commercially available 250 mg acetazolamide tablets
712 in bottles of 100. Supplies will be shipped to the study central pharmacy, which will package,
713 label, and distribute the drug kits to the sites. Sites will dispense acetazolamide at visits during
714 the 6-month randomized trial. At the 6-month visit, the subject will be given a prescription for
715 acetazolamide and it will be the subject's responsibility to obtain the drug.

716

Table 5. Composition of Acetazolamide

Component and Quality Standard (and Grade, if Applicable)	Function	Strength	
		mg/tablet	%
Acetazolamide, USP	Active drug	250.0	48.56
Lactose NF Monohydrate 200 mesh		200.0	38.85
Corn Starch NF/EP		48.0	9.32
Gelatin NF		3.2	0.62
Glycerine USP		1.6	0.31
Purified Water USP/EP (1)	N/A	(80.00)	
Talc USP		9.0	1.75
Sodium Starch Glycolate NF/EP	Binder	1.5	0.29
Magnesium Stearate NF/EP	Lubricant	1.5	0.29
Total		514.8	100

717

4.1.1.2 Storage

718

719

All study-supplied medication must be kept in a secure, safe area under recommended storage conditions as stated on the labeling with access limited to persons directly involved in the study.

720

4.1.1.3 Accountability of Acetazolamide Supplies

721

722

723

The site must maintain accurate records (including dates) of receipt, dispensing, return, and destruction of the study acetazolamide. Further details on the drug accountability process will be described in the manual of procedures.

724

4.1.1.4 Dosing and Administration

725

All subjects in the three groups will be given acetazolamide with instructions for use.

726

- The study will use 250 mg tablets of acetazolamide.

727

- Tablets will be divided into two doses, taken with meals.

728 The initial dose will be 1,000 mg twice day and then increased.

729 Beginning on Day 3, the dose will be increased by 250 mg every 2 days until a dosage of 4
730 grams daily (16 tablets) is reached (day 17) or adverse events (including side effects that
731 interfere with activities of daily living) prohibit increasing the dosage further.

732 During the titration period, subjects will be instructed to call the Site Coordinator to report any
733 intolerable adverse events. The subject may need to be seen for an unscheduled visit for clinical
734 assessment.

735 **Table 6. Acetazolamide titration schedule (number of 250 mg tablets)**

Start Day	End Day	Breakfast	Dinner	Total Daily
1	2	4	4	8 (2000 mg)
3	4	4	5	9 (2250mg)
5	6	5	5	10 (2500 mg)
7	8	5	6	11 (2750 mg)
9	10	6	6	12 (3000 mg)
11	12	6	7	13 (3250 mg)
13	14	7	7	14 (3500 mg)
15	16	7	8	15 (3750 mg)
17	--	8	8	16 (4000 mg)

736

737 If the subject is unable to tolerate the initial acetazolamide dosage, the dosage may be lowered to
738 3 tablets daily. The dosage may be subsequently decreased by one tablet every other day (or
739 sooner if the subject is substantially symptomatic) if the subject is unable to tolerate it. If the
740 subject is then able to tolerate the lower dosage, the daily dosage should be increased according
741 to the table above, or more slowly at the Site Investigator's discretion. Additional attempts to
742 increase the acetazolamide dosage beyond 17 days may be initiated at the Site Investigator's
743 discretion, but not above a total of 4 grams per day. The dosing level achieved by Day 90 will be
744 considered the subject's final dosage. This dosage will be maintained through the remainder of
745 the treatment period unless the subject improves such that the dosage can be tapered or develops
746 intolerable side effects.

747 If the acetazolamide is not tolerated at a dosage of 250 mg, then 125 mg (1/2 tablet) will be tried.
748 If this is not tolerated, furosemide will be initiated as described in section 4.1.2.

749 **4.1.1.5 Stopping the Dosage Titration**

750 The Site Investigator can stop or decrease the dosage titration if the subject has reached maximal
751 benefit (in the SI's opinion) or there is a safety concern. He/she can consult the Study co-
752 Director as necessary.

753 See section 4.1.4 below for tapering details regarding VPS group.

754

4.1.2 Addition of Furosemide

755 If a participant cannot tolerate any dose of acetazolamide or fails to improve clinically (for
756 example, worsening on the basis of: 1) subject report of progressive visual loss, 2) papilledema is
757 worsening, 3) OCT measures are worsening, 4) ETDRS acuity worsens more than 4 letters, or 5)
758 PMD worsens more than 2 dB) after 2 weeks on the maximally tolerated dosage of
759 acetazolamide, furosemide will be added, initiated at 20 mg bid. If the decision is unclear, the
760 case should be discussed with the Study co-Director.

761 The furosemide dose will be increased up to a maximum of 80 mg bid unless adverse events
762 prohibit further dosage increase, with electrolytes checked ~4 days after each dose increase.
763 After ~4 days of furosemide treatment, electrolytes will be checked (including serum sodium and
764 potassium). If sodium and potassium are normal, the dose will be increased to 40 mg bid. Again
765 after ~4 days, electrolytes will be checked and if normal the dose will again be increased to 60
766 mg bid and then if after another ~4 days and normal sodium and potassium, the dose will be
767 increased to 80 mg bid and electrolytes checked after ~4 days. Subsequently, electrolytes will be
768 checked at every visit as long as furosemide is being taken. Standard of care electrolyte testing
769 will be done at a local laboratory.

- 770 • An unscheduled visit may be needed to initiate furosemide.
- 771 • Subjects requiring furosemide will be given a prescription for the medication (the study
772 will not provide the drug). 20 meq of potassium per day will be prescribed to take
773 concomitant with furosemide and increased by 20 meq per day for each 40 mg of
774 furosemide dosed.
- 775 • If the Site Investigator determines there has been improvement with a dose of 80 mg bid
776 (160 mg/day) and expects that a higher dosage may be beneficial, the dose may be
777 increased to 100 mg bid (200 mg/day) with close monitoring for hypokalemia and
778 hyponatremia.

779

Table 7. Furosemide titration schedule (20 or 40 mg tablets may be dispensed)

Start Day	End Day	Breakfast	Dinner	Total Daily (20 mg)
1	2	1	1	2 (40 mg)
4	5	2	2	4 (80 mg)
8	9	3	3	6 (120 mg)
12	13	4	4	8 (160 mg)
*16	17	5	5	10 (200 mg)

780

781

782

*This optional dosage escalation is continued to 200 mg per day only if the Site Investigator determines there has been improvement up to this point and expects that a higher dosage may be beneficial, with close monitoring for hypokalemia and hyponatremia.

783

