348 amylase, blood dyscrasias, Stevens-Johnson syndrome, and aplastic anemia. Based on the IIHTT,
349 we anticipate that renal stones and allergic rashes will occur, though infrequently. Guidance on
350 management of liver enzyme changes and renal stones is provided in the MOP. While there was
351 minimal potassium loss in some IIHTT subjects treated with acetazolamide, there were no
352 instances of hypokalemia requiring potassium supplementation.

353 Subjects will have laboratory studies throughout the study period to monitor their electrolytes.
354 Aplastic anemia can occur in an individual by an idiosyncratic hypersensitivity reaction and
355 cannot be predicted by routine monitoring of the blood count. Some patients may be allergic to
356 acetazolamide, developing a rash (most common reaction), angioedema, stridor, or rarely,
357 anaphylaxis. A history of sulfa allergy will not be an exclusion criterion due to the lack of
358 evidence for cross reactivity with acetazolamide.⁷² The study medication will be discontinued
359 immediately if there is any evidence of an allergic reaction. At the conclusion of the subject's
360 participation in the study, their treating physician will arrange a treatment plan independent of
361 the study.

362 Hypokalemia: Epstein et al.⁷³ showed no evidence of clinically significant hypokalemia in 92
363 patients on acetazolamide unless they were also taking other diuretics. We confirmed this in the
364 IIHTT.² Since acetazolamide-induced hypokalemia is so uncommon, serum electrolytes will be
365 obtained at 1 month, 4 months, and 6 months (unless subjects develop symptoms of
366 hypokalemia: weakness, fatigue, and muscle cramps). If a subject also requires treatment with
367 furosemide, he/she will have close monitoring of serum electrolytes (including serum sodium
368 and potassium) prior to each change in dosage, to be performed at a local laboratory. The dosage
369 of furosemide will not be increased until it is documented that the potassium level is in the
370 normal range. Once the final furosemide dosage has been reached, electrolytes will be checked at
371 each visit.

372 Aplastic Anemia: Acetazolamide-induced aplastic anemia is dosage independent, usually
373 delayed in onset, and usually fatal. According to prior studies^{74,75}, the incidence has been
374 estimated as 1 per 15,000 patient years with a mean age of 71 years (range 56-86 years). The

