1135 through the Week 8 visit in order to provide masking to VPS. The use of a standardized visual
1136 field protocol should limit the influence of the visual field technician on the results of the
1137 examination.

1138 **6.6 OCT**

1139 Spectral-domain OCT evaluations of the optic nerves, peripapillary RNFL, and macula will be
1140 obtained using a Cirrus™ (Carl Zeiss-Meditec, Inc, Dublin, CA) or Spectralis® (Heidelberg
1141 Engineering, Inc, Carlsbad, CA) spectral-domain OCT. The subject must have the same brand of
1142 OCT machine used for data collection at each visit.

1143 **6.7 Lumbar Puncture**

1144 Lumbar puncture is performed as part of usual care at baseline. Although repeat lumbar puncture
 1145 is not considered standard of care, subjects will undergo a second voluntary lumbar puncture for
 1146 CSF opening pressure measurement at the 6-month visit, following the procedure detailed in the
 1147 MOP.

1148 **6.8 Quality of Life Assessment**

1149 The NEI VFQ-25 and the 10-item Neuro-ophthalmic Supplement to the VFQ-25 will be used, as
 1150 well as the SF-36v2.⁷⁹ Testing time is approximately 20 minutes.

1151 **6.9 Headache Disability Rating**

1152 Headache disability will be rated using the HIT-6 (Headache Impact Test),⁸⁰ a 6-item scale that
 1153 is commonly used to rate migraine disability and has been validated for IHH. Testing time is 1-2
 1154 minutes.

1155 **6.10 Neurologic and Physical Examination**

1156 A standard neurological evaluation will be performed at screening. When indicated, a general
 1157 medical examination will be performed.

1158 **6.11 Clinical Laboratory Tests**

1159 CBC with platelet count will be obtained at Baseline and at Weeks 16 and 26 for all subjects.

1160 A comprehensive metabolic profile, including liver function tests, electrolytes, and amylase, will
 1161 be obtained at Baseline and at Weeks 16 and 26 for all subjects.

1162 For subjects taking furosemide, serum potassium and sodium levels will be checked prior to each
 1163 dosage change, after reaching the maximum tolerated dosage, and then at each subsequent visit.

1164 This testing will be performed at a local laboratory.

1165 Routine clinical laboratory tests will be performed locally by the site or the subject's local
 1166 laboratory if travel to the site is not convenient. The Site Investigator will review the laboratory
 1167 values. The Site Investigator will prescribe appropriate supplementation for hypokalemia,

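### Furosemide Table 7 disagrees with the section 4.1.2 text on days covered, first interval and electrolyte condition, and its tablet counts fit only one of the two strengths its title allows

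*Protocol*

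**What the plan says.** **Prose of Protocol 4.1.2.** For a participant who cannot tolerate acetazolamide, or who fails to improve on it, "acetazolamide, furosemide will be added, initiated at 20 mg bid". The first laboratory check is then set: "After ~4 days of furosemide treatment, electrolytes will be checked (including serum sodium and" potassium). The first increase depends on the result: "If sodium and potassium are normal, the dose will be increased to 40 mg bid". The same pattern leads to 60 mg bid and 80 mg bid at steps of about 4 days. A further step to 100 mg bid is optional. After that, electrolytes are checked at each visit while the drug is taken.

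**Table 7, same section.** The title is "Furosemide titration schedule (20 or 40 mg tablets may be dispensed"). There are five rows with a start day, an end day, breakfast and dinner tablet counts, and a total column headed "Total Daily (20 mg"). The last row is footnoted: "This optional dosage escalation is continued to 200 mg per day only if the Site Investigator" judges that there has been improvement and expects benefit from more. No electrolyte condition appears between the rows.

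**Elsewhere in the protocol.** Section 1.5.1.2, under hypokalemia, says that the dosage "of furosemide will not be increased until it is documented that the potassium level is in the" normal range. Section 6.11 says: "For subjects taking furosemide, serum potassium and sodium levels will be checked prior to each" dosage change. Footnote 5 to the visit schedule in 1.8.1 also places testing before each dose increase. The Protocol Summary gives 160-200 mg per day as the top of the titration, and section 1.3.2.1 gives 80-100 mg twice daily.

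**The concern.** A titration table is what a site is likely to work from, so it should be usable as printed. Table 7 is not. It leaves days blank between steps, it has no continuing row after the last step, and it leaves out the laboratory result on which each step depends. It also offers two tablet strengths with one set of counts.

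This drug needs that precision. Section 1.5.1.3 calls hypokalemia furosemide's most common important side effect, and section 9.8.1 lists it among the events of particular concern to the DSMC. Furosemide is prescribed and not supplied by the study (4.1.2), so the study does not control the strength dispensed. The pill counts in 4.1.3 cover acetazolamide only and would not reveal a furosemide tablet error.

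A lesser consequence is uneven delivery of medical therapy if sites read the table differently.

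**Working it through.** **Inputs.** Table 7 rows as printed; the prose steps of 4.1.2 (20, 40, 60, 80 and optionally 100 mg bid, at intervals of about 4 days); Table 6 in 4.1.1.4 for comparison of format.

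**Step 1: reproduce the printed totals.** Total = (breakfast + dinner tablets) x 20 mg.

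| Days | Tablets per day | x 20 mg | Printed | x 40 mg |
|---|---|---|---|---|
| 1-2 | 1 + 1 = 2 | 40 | 40 | 80 |
| 4-5 | 2 + 2 = 4 | 80 | 80 | 160 |
| 8-9 | 3 + 3 = 6 | 120 | 120 | 240 |
| 12-13 | 4 + 4 = 8 | 160 | 160 | 320 |
| 16-17 (optional) | 5 + 5 = 10 | 200 | 200 | 400 |

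All five printed totals are reproduced with 20 mg tablets. The dose levels also match the prose.

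**Step 2: days covered.** Five rows x 2 days = 10 days, and 17 - 10 = 7 days without a listed dose (3, 6, 7, 10, 11, 14, 15), or 7/17 = 41%. Without the optional row, 4 x 2 = 8 days are covered, and 13 - 8 = 5 are not (3, 6, 7, 10, 11). Blank days between rows = next start - previous end - 1:
- 4 - 2 - 1 = 1
- 8 - 5 - 1 = 2
- 12 - 9 - 1 = 2
- 16 - 13 - 1 = 2

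The same calculation on Table 6 gives 0 between every pair of rows, and its last row starts on day 17 with no end day. Every row of Table 7 has an end day.

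**Step 3: intervals between dose starts.** 4 - 1 = 3; 8 - 4 = 4; 12 - 8 = 4; 16 - 12 = 4. Three of the four equal the prose interval. The first is one day shorter than about 4 days.

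**Step 4: the counts read as 40 mg tablets.** The last column of the table above is twice the printed dose in every row. Three rows (240, 320 and 400 mg/day) exceed the stated upper limit of 200 mg/day.

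**Step 5: the printed doses made from 40 mg tablets.** Tablets per intake = mg per intake / 40:
- 20/40 = 0.5
- 40/40 = 1
- 60/40 = 1.5
- 80/40 = 2
- 100/40 = 2.5

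Three of the five steps (20, 60 and 100 mg bid) cannot be made from whole 40 mg tablets, and the table shows no half-tablet counts.

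**The case against.** The best defence is that Table 7 summarises the prose beside it and that the two, read together, leave little room for harm. A reader might draw three stronger conclusions, and the documents support none of them.

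- **That the protocol prescribes on-off dosing, or stopping on day 13 or 17.** No section calls for dose-free days. Section 4.1.2 speaks of continued electrolyte checks while the drug is taken, 4.1.4 provides a taper, and the schedule in 1.8.2 lists furosemide prescribing as needed at weeks 52 and 104. The blanks come from the end-day column and are not a treatment instruction.
- **That the table directs escalation ahead of the laboratory check.** Only the first interval is short, by one day against an approximate figure. The condition is stated in the prose directly above the table, and again in 1.5.1.2 and 6.11. The table is silent on it but does not override it.
- **That the table doubles the dose.** The total column is headed "Total Daily (20 mg"), every row prints its mg total, and the prose gives each step in mg. Doubling needs someone to take the unlabelled breakfast and dinner counts alone and apply them to 40 mg tablets.

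It is also fair to say that the effect on the comparison of arms is limited. Medical therapy, with furosemide where needed, belongs to all three arms, and only participants who do not improve on acetazolamide or cannot tolerate it receive furosemide.

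All of this stands, and it limits the point to one of consistency and clarity. It does not make the table usable as printed: the blank days, the missing continuation, the missing condition and the unmatched 40 mg option all remain.

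**Conclusion.** The point holds as an inconsistency between an operative dosing table and its own text. Its size:

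- 7 of 17 days without a listed dose (5 of 13 without the optional step), and no open-ended row.
- A first interval of 3 days against about 4, with the other three in agreement.
- No electrolyte condition shown, although three sections require a check or a normal result before an increase.
- A 40 mg option with no matching counts. If the counts were misread, the dose would be twice the printed one, and three of five rows would be above 200 mg/day.

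The doubling is conditional on a misreading; the other items are on the page.

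Two assumptions apply. First, the table is taken as printed. Each row ends exactly one day after it starts, and that regularity makes damage in text extraction unlikely. Second, the manual of procedures is not among the documents and may already give fuller instructions.

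There is no bearing on alpha, power, sample size or the primary analysis. The reason to act is participant safety and uniform conduct across sites.

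**What to change.** Reconcile Table 7 with the 4.1.2 text so that they agree on four things: the day ranges, what continues after the last step, the electrolyte condition between steps, and the tablet strength or strengths. Show each step in mg per intake, or give counts labelled by strength. Check the result against 1.5.1.2, 6.11 and footnote 5 of 1.8.1. Which schedule, step length and dose stand is for the sponsor to decide.

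The cost is one corrected table and a memo to sites, plus the same correction in the manual of procedures if it repeats the table. If the reconciled version keeps the laboratory checks already required, it adds no visits or tests.

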815 utilized (see MOP more details). The surgery will make a window in the dural sheath of at least 4
816 mm in length under the operating microscope. The procedure will be considered successful if
817 CSF egress is noted at the time of fenestration. Post-operative visits will be performed according
818 to the surgeon's usual routine.

- 819 • If both eyes meet study entry criteria, ONSF will be performed on the eye with the worst
820 PMD first, ideally within three days of randomization. If the other eye still meets eye-
821 level eligibility criteria at two weeks after surgery on the first eye, ONSF will be
822 performed on the second eye. If the second eye improves at two weeks after surgery on
823 the first eye and no longer meets eligibility criteria, ONSF will not be performed on that
824 eye.
- 825 • If only one eye meets entry criteria as an eligible eye, ONSF will be performed on the
826 eligible eye ideally within three days of randomization.
 - 827 ♦ If the second eye is not eligible for the study because visual field MD is too good, but
828 the eye worsens (i.e. PMD -6 dB or worse with size V perimetry at any time during
829 study follow-up), ONSF will be performed on the non-eligible eye. Also, if the non-
830 eligible eye meets criteria for temporary treatment failure (see section 5.6.3 below), it
831 will be operated on even if the PMD is not worse than -6 dB.
 - 832 ♦ If the second eye is not eligible for the study because visual loss is too severe, ONSF
833 will be considered at two weeks after surgery on the eligible eye.

834 See section 4.6, Management of the Non-Eligible Eye, for exceptions.

835 Administration of intravenous and topical corticosteroids is permitted intra-operatively, but
836 systemic corticosteroids are not to be administered post-operatively (see MOP for details).
837 Medical therapy will be continued until the Site Investigator believes that the dosage should be
838 stopped or decreased because the subject has improved; he/she may contact the Study co-
839 Director to decide on how to proceed. See section 4.1.4, Tapering of Medical Therapy.

842 **4.3 CSF Shunting**

843 CSF shunt surgery will occur ideally within 3 days of randomization by a certified neurosurgeon.
844 See MOP for surgeon qualifications. Using a frameless image-guided stereotactic system, a
845 ventricular shunt catheter will be positioned in the lateral ventricle of the cerebral hemisphere not
846 associated with speech. The ventricular catheter will be connected to an adjustable valve and the
847 distal shunt system will be placed in the peritoneal cavity. Post-operative computed tomography
848 of the brain will be obtained to confirm shunt tip placement. Post-operative visits will be
849 performed according to the surgeon's usual routine.

850 Since the purpose of this procedure is to normalize CSF pressure, the Site Investigator will taper
851 medical therapy at the time of the surgery and then further if/when he/she is confident that the
852 VPS is working (see section 4.1.4, Tapering of Medical Therapy).

853 **4.4 Prohibited Medications, Treatments, and Procedures**

854 Corticosteroids, topiramate, methazolamide, and additional diuretics (other than furosemide)
 855 may not be used during the study period (except intra-operative corticosteroids with ONSF).
 856 Should a subject begin an excluded treatment during the trial, this will be reported on a visit or
 857 phone contact form. The Study Director/co-Director will determine whether there is a potential
 858 safety risk and whether study treatment needs to be discontinued.

859 Other treatments for IIH, including bariatric surgery and transverse sinus stenting, will not be
 860 allowed during the first six months.

861 **4.5 Concomitant Medications**

862 **4.5.1 Allowed Concomitant Medications**

863 All concomitant medications must be used in accordance with approved labeling and as
 864 prescribed unless they are commonly used off-label for the prescribed purpose.

865 Headaches may persist as a major management problem in IIH patients after study treatments
 866 have been given.^{82,83} The headache can be treated with standard prophylactic vascular headache
 867 remedies: non-steroidal anti-inflammatory drugs and tricyclic antidepressants may be effective.
 868 Low dosage amitriptyline is suggested; the initial dosage will be 10 mg at bedtime, gradually
 869 increasing to a maximum of 50 mg at bedtime, if needed. Weight gain is a well-known side
 870 effect of amitriptyline; by using a low dosage and monitoring the subject's weight, we anticipate
 871 minimizing this untoward effect. Acute headache may be treated with non-steroidal anti-
 872 inflammatory drugs (naproxen 500 mg bid), but their use will be limited to no more than three
 873 days per week to prevent analgesic rebound (medication overuse) headache. Table 8 below gives
 874 the Site Investigator a group of medications from which to choose. These medications should not
 875 be used more than 3 days per week.

876 **Table 8. Medications available for the symptomatic treatment of headache.**

Medication*	Maximum Daily Dosage**
Naproxen sodium	1 gram
Acetaminophen	1500 mg
Aspirin	1950 mg
Ibuprofen	1600 mg
Acetaminophen with codeine 30 mg	4 tablets
Butalbital/APAP or Butalbital/ASA	4 tablets

877 * Acetaminophen, aspirin, and non-steroidal anti-inflammatory drugs are preferred.

878 ** Symptomatic treatment should be limited to 3 times weekly or less to prevent
 879 analgesic rebound (medication overuse) headache. Subjects requiring symptomatic
 880 headache treatment more than 3 times per week should be prescribed a preventive
 881 medication.

882 There is no single agent that will be effective and tolerated by all subjects needing prophylactic
 883 headache therapy. Table 9 below takes into consideration the undesirable side effects of many
 884 available agents for headache prevention. Gabapentin has few drug interactions, but may

885 increase the serum concentration of barbiturates and morphine. The selective serotonin reuptake
 886 inhibitors may produce a small amount of weight gain within the first year of usage. Protriptyline
 887 is the least sedating of the tricyclic antidepressants and is least likely to produce weight gain of
 888 medications in this class, but also may not be as effective at headache relief.

889

Table 9. Preventive medications for headache.

1 st -Tier Medications	
Medication	Suggested Starting and Final Dosages
Amitriptyline	10 mg qhs, up to 50 mg qhs if needed*
Vivactil™ (protriptyline)	5 mg qhs, up to 10 mg bid if needed*
Naproxen	Up to 1 gram daily in divided doses
Nortriptyline	25 mg qhs
* May be associated with weight gain; monitoring required	
2 nd -Tier Medications	
Medication	Suggested Starting and Final Dosages
Gabapentin	100 mg qhs, up to 400 mg TID if needed
Fluoxetine	20 mg daily

890 Subjects already taking preventive medication for headache at study entry may continue using
 891 their preventive medication *unless they are taking topiramate*. It is uncertain if the carbonic
 892 anhydrase inhibition associated with topiramate is sufficient to have potential therapeutic value
 893 in IHH; this could confound the results of the study.

894

